2.5.3 Handling of missing values/censoring/discontinuations

The handling of missing data has been described for each endpoint in [Section 2.5.1](#). The missing value due to discontinuation will not be imputed.

2.6 Safety analyses

The safety and tolerability of MIJ821 will be evaluated by adverse events, clinical significant findings from laboratory test, physical examination, vital signs, 12-lead ECG, holter ECG and safety scales.

Unless otherwise stated, the safety data listed in following subsections will be analyzed separately for Core Period based on SAF and Retreatment Period based on RTS. For the summary of change from baseline in Retreatment Period, the baseline will be the last valid assessment before retreatment, i.e. the baseline of retreatment.

2.6.1 Adverse events (AEs)

Treatment-Emergent Adverse Events (TEAEs) are defined as adverse events starting or worsening after the first dose of study medication and up to 2 weeks post the last dose. For relapsed participants who receive retreatment of MIJ821 in Extension Period, adverse events starting after 2 weeks post the last dose of Core Period up to the start of retreatment will not be counted as TEAEs. The missing onset date of AE will be imputed before identify the TEAE (see imputation rule in [Appendix 5.1.1](#))

The Medical Dictionary for Regulatory Activities (MedDRA) version 24.0 or later will be used to code Adverse Event (AE) to a SOC and a PT.

TEAEs will be analyzed separately for Core Period and Retreatment Period:

- The summary of TEAEs in Core Period (up to 2 weeks post the last dose) will be based on SAF
- The summary of TEAEs in Retreatment Period (up to 2 weeks post the last dose of retreatment) will be based on RTS

The number (and percentage) of participants with TEAEs will be summarized by following approach as defined in [Table 2-7](#), in terms of all TEAEs, Treatment-Emergent Serious Adverse Events (TESAEs), TEAEs leading to treatment discontinuation, treatment-related TEAEs or TESAEs and death:

- by treatment, primary system organ class and preferred term
- by treatment, primary system organ class, preferred term and maximum severity
- by treatment, Standardized MedDRA Query (SMQ) and preferred term
- by treatment, preferred term with most frequent (incidence rate $\geq 5\%$)

Table 2-7 AE Summaries of Subject Incidence

Category	by SOC and PT	by SOC, PT and maximum severity	by most frequent PT (≥ 5%)
All TEAEs	Y	Y	Y
TESAEs	Y		
AEs leading to treatment discontinuation	Y		
Treatment-related TEAEs	Y		
Treatment-related SAEs	Y		
Deaths	Y		

For all AEs tables presented by SOC and PT (and grade), the SOC's will be presented in alphabetical order and PTs will be ordered within the SOC by decreasing order of frequency. AE tables by preferred term only will be sorted in descending order of frequency.

A participant with multiple adverse events within a primary system organ class is only counted once towards the total of the primary system organ class.

All AEs, deaths, SAEs and AEs leading to permanent study drug discontinuation will be listed separately.

For clinical trial safety disclosure to ClinTrials.gov (CT.GOV) and European Union Drug Regulating Authorities Clinical Trials (EudraCT) at end of study, following summaries will be provided.

Table 2-8 Clinical Trial Safety Disclosure Requirements

	Requirements	CT.GOV	EudraCT
SAE	Number of subjects who had treatment emergent / on-treatment SAE	Y	Y
	Number of subjects who had on-treatment death	Y	Y
	Number of subjects who had on-treatment death due to SAE that were causally related to treatment		Y
	Number of SAEs by SOC/PT	Y	Y

	Number of occurrences of SAEs by SOC/PT		Y
	Number of occurrences of SAEs that were causally related to treatment by SOC/PT		Y
	Number of SAEs, with outcome of death, related to treatment/all by SOC/PT		Y
NSAE	Number of subjects who had treatment emergent / on-treatment Non-SAE(NSAE) with 0-5% threshold	Y	Y
	Number of NSAEs (0-5% threshold) by SOC/PT	Y	Y
	Number of occurrences of NSAE with 0-5% threshold by SOC/PT		Y

2.6.1.1 Adverse events of special interest / grouping of AEs

Based on the current available information, following events are considered Adverse Events of Special Interest (AESI). This information is subject to change, based on the availability of incremental clinical experience with MIJ821. MedDRA search criteria for AESIs will be identified by the latest version of electronic Compound Case Retrieval Strategy (CRS).

- Dissociation
- Sedation
- Cardiovascular effects (BP changes and QT interval prolongation on ECG)
- Respiratory effects (difficulty in breathing, changes in oxygen saturation)
- Suicidality (suicidal ideation or behavior)
- Memory gaps/ amnesia
- Cystitis or other lower urinary tract adverse events

AESI will be summarized by risk name and PT respectively for Core Period and Retreatment Period. The time to onset on each dosing day, starting from first dosing, starting from the most recent dosing and time to resolution (starting from first onset date) of each AESI at risk level will be summarized by descriptive statistics. For multiple AESIs per subject, the earliest onset time and the latest resolution time will be counted per subject. For AESI occurred on dosing day, a listing will be provided with the time to onset (starting from first dosing, starting from the most recent dosing) and time to resolution (starting from onset date) by risk name and PT term for each participant. AESIs occurred on non-dosing days will be presented by listing in similar manner.

In addition, the by AESI category as listed above and by PT summary will be provided for AESI identified by investigator and reported in CRF AE form under the Adverse Event Category of "Adverse event of special interest". A listing will be provided as well.

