### 3.2 Double-blind Core Period

The double-blind Core Period starts on Day 1 and lasts 6 weeks. All baseline assessments (including the primary efficacy scale MADRS) must be performed on Day 1, prior to randomization. Investigational drug will be administered in a double-blind manner in the form

of a 40-minute intravenous infusion on Day 1, Day 15 and Day 29. Designated unblinded qualified site personnel is required for the preparation of the infusion prior to administration.

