Analysis of AEs of interest showed that dissociative side effects, sedation and amnesia (investigator reported) were seen at both the 0.16 mg/kg and 0.32 mg/kg MIJ821 doses. Amnesia in particular was dose dependent and more common at the higher MIJ821 dose (42.1% with MIJ821 0.32 mg/kg vs 9.5% with MIJ821 0.16 mg/kg pooled doses). No AEs of amnesia was seen in Ketamine or Placebo arms. About one-quarter of patients in each active treatment group experienced dissociative side effects (23.8% for 0.16 mg/kg pooled dose and 26.3% in 0.32 pooled mg/kg dose), versus 50% with Ketamine and 10% with placebo. Sedation was seen at both active doses (14.3% at the lower pooled dose and 21.1% at 0.32 mg/kg pooled dose vs 10% with ketamine and 0% with placebo).

Time to onset of dissociative side effects, amnesia and sedation was short, occurring within the 40 minutes of infusion in most cases for both MIJ821 doses and for placebo, though somewhat longer than with ketamine. Median time to onset for adverse event of sedation was shorter for the lower MIJ821 dose (pooled 0.16 mg/kg dose, 0.25 hours) than the higher dose (pooled 0.32 mg/kg dose, 1.46 hours), versus 0.10 hours for ketamine and no cases (0.0 hours) for placebo.

Most events of amnesia resolved within 4 hours (median time to resolution was 3.27 hours). Median time to resolution for dissociation ranged from 5.25 hours for MIJ821 0.16 mg/kg

pooled dose versus 3.72 hours for MIJ821 0.32 mg/kg pooled dose, and shorter times for ketamine (1.02 hours) and placebo (2 hours). Events of sedation resolved faster for the pooled 0.16 mg/kg dose than 0.32 mg/kg pooled dose (median time 1.6 hours vs 2.5 hours). Ketamine time to resolution was 0.47 hours.

At both MIJ821 investigated doses, increases in mean supine systolic and diastolic blood pressure were observed at the first sampling time of 1 hour after start of the 40 min infusion. The placebo-adjusted mean change from baseline in supine SBP and DBP appeared to peak between 2 to 4 hours after start of infusion ( $< 20$  mmHg) with a clear trend of recovery to baseline within 4 hours (DBP) and 6 hours (SBP) after start of infusion.

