### 6.1.3 Treatment arms/group

This study consists of seven treatment arms, participants will be randomized in a 2:1:2:2:2:2:2 ratio on Day 1 to the following treatment arms on the top of the ongoing SoC:

- Placebo, one infusion every other week on Day 1, Day 15 and Day 29 of treatment (Core Period only)
- MIJ821 fixed dose of 0.0048 mg/kg, one infusion every other week on Day 1, Day 15 and Day 29 of treatment/ relapse retreatment
- MIJ821 fixed dose of 0.016 mg/kg, one infusion every other week on Day 1, Day 15 and Day 29 of treatment/ relapse retreatment
- MIJ821 fixed dose of 0.048 mg/kg, one infusion every other week on Day 1, Day 15 and Day 29 of treatment/ relapse retreatment
- MIJ821 fixed dose of 0.16 mg/kg, one infusion every other week on Day 1, Day 15 and Day 29 of treatment/ relapse retreatment
- Single administration MIJ821 0.048 mg/kg, one infusion on Day 1, followed by placebo infusions every other week on Day 15 and Day 29 of treatment / relapse retreatment
- Single administration MIJ821 0.16 mg/kg, one infusion on Day 1, followed by Placebo infusions every other week on Day 15 and Day 29 of treatment / relapse retreatment

In all treatment arms, investigational treatment will be administered by intravenous infusion every other week, 3 infusions in total during the placebo-controlled double-blind Core, 6-week period of the study.

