Clinical Development

MIJ821

CMIJ821A12201 / NCT04722666

A double-blind, placebo-controlled, randomized dose-ranging trial to investigate efficacy and safety of intravenous MIJ821 infusion in addition to comprehensive standard of care on the rapid reduction of symptoms of Major Depressive Disorder in Subjects who have suicidal ideation with intent

Statistical Analysis Plan (SAP)

Document type: SAP
Document status: Amendment v1 Final
Release date: 30-Jun-2023
Number of pages: 55

Property of Novartis
For business use only
May not be used, divulged, published or otherwise disclosed
without the consent of Novartis
Template Version 3.0, Effective from 01-Jul-2020

Document History – Changes compared to previous final version of SAP

Date	Major updates and reason	Section and title impacted (Current)
14-Jun-2021	First version	
30-Jun-2023	Amendment 1 final	
	Added MIJ821 PK analysis in CSR SAP since it's one of secondary endpoints	Section 2.1.3 Analysis sets Section 2.7 PD and PK/PD analyses
	Defined Randomized Set for population description; defined Extension Set for follow-up data analysis	Section 2.1.3 Analysis sets
	For the supplementary estimand, changed the missing data imputation approach from J2R to MAR under treatment policy. Because MIJ821 will sustained effect after 1st dosing for a while, so J2R is scientifically inappropriate.	Section 2.4.5 Supplementary analysis
	Removed summary of MADRS, [REDACTED]	Section 2.4.6 Supportive analysis Section 2.10.1 Effect on depression mood Section 2.10.2 Effect on suicidality
	Added KM analysis for time to relapse;	Section 2.5.2 Statistical hypothesis, model, and method of analysis
	Added logistic regression model with firth method as the alternative model to repeated logistic regression model if not converged due to zero count	Section 2.10.2 Effect on suicidality

Date	Major updates and reason	Section and title impacted (Current)
	Added the summary of time to onset and time to resolution for AESIs if onset on dosing day, and since most recent dose.	Section 2.6.1.1 Adverse events (AEs)
	Added the change from most recent dose in terms of ECG parameters; Removed summary for holter due to data is not supportive for it	Section 2.6.4.1 ECG and cardiac imaging data
	Added the change from most recent dose for SBP/DBP	Section 2.6.4.2 Vital Signs
	[REDACTED]	[REDACTED]
	[REDACTED]	[REDACTED]
	[REDACTED]	[REDACTED]
	[REDACTED]	
	[REDACTED]	
	[REDACTED]	
	[REDACTED]	
	[REDACTED]	[REDACTED]
	[REDACTED]	[REDACTED]

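### SAP 2.6.1.1 times AESI resolution from a participant's first onset to the latest resolution within a period, so symptom-free time between infusions counts as duration when episodes recur

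*SAP*

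**What the plan says.** SAP 2.6.1.1 plans descriptive statistics for AESI timing. Time to onset is measured in several ways: on each dosing day, from the first dose and from the most recent dose. For resolution there is one definition: "time to resolution (starting from first onset date) of each AESI at risk level will be summarized by descriptive statistics". The next sentence deals with participants who have several events: "For multiple AESIs per subject, the earliest onset time and the latest resolution time will be counted per subject". The reporting span is set earlier in the same paragraph: "AESI will be summarized by risk name and PT respectively for Core Period and Retreatment Period".

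The same section also plans participant listings, one for AESIs on dosing days and a similar one for other days. The dosing-day listing gives "time to resolution (starting from onset date) by risk name and PT term for each participant", so the word *first* is in the definition for the summary but not in the one for the listing.

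Each period can hold three infusions. In the Core Period, study drug is given in the form "of a 40-minute intravenous infusion on Day 1, Day 15 and Day 29". The two single-infusion arms receive active drug only at the first of these, for example "Single administration MIJ821 0.16 mg/kg, one infusion on Day 1, followed by Placebo infusions every other week on Day 15 and Day 29" (Protocol 6.1.3).

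**The concern.** Protocol 4.5 (Clinical Safety) describes dissociation, sedation and amnesia as short-lived, with onset in most cases during the infusion and resolution within hours. Such episodes can recur after a later infusion. A span from first onset to last resolution then joins separate episodes and records the well time between them as time with the event.

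The distortion would not fall equally on the arms. A repeat-dose arm has three active infusions that can trigger an episode; a single-infusion arm has one. A table of AESI duration by arm could therefore show a regimen difference even if every episode lasted equally long. Protocol 4.5 and 10.2.5 also expect most events of interest to resolve within the four-hour observation period. Time to resolution is the natural summary for checking that expectation, and under this rule it would not do so for participants who recur.

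**Working it through.** The documents state no figure for this rule, so there is none to reproduce. The check applies the rule to the protocol's own timings.

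**Inputs**
- Infusions on Days 1, 15 and 29 (Protocol 3.2): gaps of 14 days (336 h) between adjacent infusions and 28 days (672 h) between the first and third.
- Median episode length *d* in the proof-of-concept study (Protocol 4.5, Clinical Safety): sedation 1.6 h and dissociation 5.25 h at pooled 0.16 mg/kg; amnesia 3.27 h.
- Dissociation incidence in that study: 23.8% at pooled 0.16 mg/kg and 10% on placebo.
- 30 participants randomised per arm, except the lowest dose (Protocol 12.8.1).
- Probability of recurrence at a later infusion: not in the documents. It is an assumption, shown as a range.

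**Step 1: one participant.** With the same onset delay and length after each infusion, recorded duration = gap between first and last affected infusion + *d*.

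| Event | One episode | Two adjacent infusions (336 + *d*) | Infusions 1 and 3, or all three (672 + *d*) |
|---|---|---|---|
| Sedation | 1.6 h | 337.6 h | 673.6 h |
| Amnesia | 3.27 h | 339.27 h | 675.27 h |
| Dissociation | 5.25 h | 341.25 h | 677.25 h |

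The last two columns are about 14 and 28 days. For dissociation, 677.25 / 5.25 = 129 times the episode length.

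**Step 2: one arm.** 0.238 × 30 = 7.14, so about seven participants would contribute a dissociation time in a 0.16 mg/kg arm. If one of the seven has episodes at infusions 1 and 3, the mean is (6 × 5.25 + 677.25) / 7 = 101.25 h and the maximum is 677.25 h. The median stays at 5.25 h.

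**Step 3: range over recurrence.** Take participants with dissociation at infusion 1, and let *r* be the probability of an episode at each later infusion, independently. The share recorded at about 28 days is *r*, at about 14 days *r*(1 − *r*), and at either 1 − (1 − *r*)². The mean is 672*r* + 336*r*(1 − *r*) + 5.25. For the placebo infusions of a single-infusion arm, spreading the 10% placebo incidence over three infusions gives *r* = 1 − 0.90^(1/3) = 0.0345. That spread, and the use of 5.25 h for a placebo episode, are simplifying assumptions.

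| Arm | *r* | About 28 d | About 14 d | Either | Mean |
|---|---|---|---|---|---|
| Repeat-dose | 0.10 | 10% | 9% | 19% | 103 h |
| Repeat-dose | 0.25 | 25% | 19% | 44% | 236 h |
| Repeat-dose | 0.50 | 50% | 25% | 75% | 425 h |
| Repeat-dose | 0.75 | 75% | 19% | 94% | 572 h |
| Single-infusion | 0.0345 | 3.5% | 3.3% | 6.8% | 40 h |

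The episode length is 5.25 h in every row. The median reaches weeks only when 1 − (1 − *r*)² exceeds 0.5, that is *r* > 1 − √0.5 = 0.29.

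**Step 4: after the change.** Timed from its own onset to its own end, each episode returns 5.25 h (or 1.6 h, or 3.27 h) in every arm, whatever the number of infusions that triggered one.

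**The case against.** The strongest reply is that the unit of analysis may be the dosing day. The SAP's document history describes the addition as "Added the summary of time to onset and time to resolution for AESIs if onset on dosing day, and since most recent dose", and the summary sentence itself opens with onset on each dosing day. If the rule for several AESIs were meant within one dosing day, earliest onset to latest resolution would be sensible. But the section that governs the tables writes no reset at each infusion for resolution. It specifies the first onset date, where the listing specifies the onset date. The change-log wording is a hint of intent and does not override that. If a per-dose calculation was intended, the same correction puts it into the text.

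Several other points on that side stand:

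- The documents give no recurrence rate. In the first-in-human study, dissociative and cognitive events under repeated dosing were seen in only two participants, at 0.32 mg/kg, above any dose used here. Recurrence may be uncommon.
- A reader might infer from the roughly 24% incidence of dissociation that arm medians will move to weeks. Incidence says nothing about recurrence among those affected, so the inference fails.
- A summary per participant and a listing per event differ in unit. That alone is not a contradiction, and the listings keep the correct durations in view.
- The earliest-onset convention is appropriate for time to first onset and should survive.

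**Conclusion.** The rule as written gives wrong durations for any participant whose transient AESI recurs at a later infusion in the same period, and it should be fixed. The error is about 14 days for adjacent infusions and about 28 days when infusions 1 and 3 are both affected. It is nil for a single episode, and Core and Retreatment are never joined. Means and maxima are inflated by any recurrence; medians only if about half or more of those affected recur.

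That repeat-dose arms are affected more is an inference from the design. Its size rests on the assumed recurrence range and on independence between infusions.

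Two stronger readings are not supported. First, a reader might conclude that the error would drive the choice of dose and regimen at the interim analysis. Protocol 4.4 and 12.7 and SAP 2.11 refer only to safety results or the safety profile; no decision rule uses AESI duration, and the secondary safety endpoint, number and severity of TEAEs, is untouched. Second, a reader might conclude that the results could not be compared with the proof-of-concept medians. The documents do not say how those were derived, so this cannot be settled from them. What is distorted is a descriptive comparison of AESI duration between regimens.

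**What to change.** In SAP 2.6.1.1:

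- Define time to resolution as each episode's end minus that episode's own onset, in the summary as well as the listings.
- For AESIs with onset on a dosing day, summarise by infusion, with one value per participant per infusion (for example the longest episode).
- For AESIs not tied to an infusion, which may include suicidality or lower urinary tract events, summarise per episode.
- Keep earliest onset for time to first onset. Remove the earliest-onset to latest-resolution span for time to resolution.

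The cost is a few lines of SAP text and minor programming. The onset and resolution times are already needed for the planned listings, so no new data are required.

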2.6.2 Deaths

Deaths will be listed by actual treatment arm including the start date of the study treatment, the last dose date on study treatment, the death date and the primary cause (and contributing cause if any) for death.

2.6.3 Laboratory data

For Core Period up to 2 weeks' follow up visit, and separately for the Retreatment Period, following analyses will be provided for laboratory data by treatment arm and analysis visit:

- Average change from baseline of laboratory hematology, blood chemistry results in forms of table.
- The number and proportion of participants with newly occurring or worsening clinical abnormality (outside normal range). For newly occurring event, the participant needs to have a baseline value that is not clinically abnormal for that parameter. For participant with missing baseline value, any post-baseline abnormal value will be considered as newly occurring. For worsening event, the participant needs to have a baseline value that is clinical abnormal and also have a worse post-baseline value.
- Listing of participants with abnormal laboratory values.

To evaluate the potential drug-induced hepatotoxicity and renal signal, the liver and renal abnormalities will be analyzed by:

- the number and proportion of participants with any liver enzyme abnormalities based on each criteria defined in [Table 5-3](#) in Appendix.
- the number and proportion of participants with any renal abnormalities based on each criteria defined in [Table 5-4](#) in Appendix.
- listings of participants with clinically liver or renal abnormality.

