### **Clinical laboratory evaluations**

Summary statistics will be provided by visit/time point and treatment. Shift tables using the low/normal/high/ (low and high) classification based on predefined limits will be used to compare baseline to the worst on-treatment value. Notable abnormal laboratory data will be listed by treatment group, participant, and visit if limits are available.

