The main analyses will summarize data collected in Core Period up to 2 weeks follow up in Extension Period. The monthly follow-up visit in Extension Period will not be presented in by-visit summary, unless otherwise specified.

In addition for participants who are retreated during Extension Period, assessments performed during Retreatment Period will be mapped to the analysis visit according to [Table 2-3](#).

Table 2-3 Analysis Visit Windows for Retreatment Period

Analysis Period	Study visit	Target Day since start of retreatment*	Day since start of retreatment*
Retreatment Period	Baseline of Retreatment	Day 1 -2 hours pre-retreatment (See definition for	1

		baseline of retreatment in Section 2.1.1)	
	Retreatment D1 40 min, 2 h, 4 h	Day 1 40 min, 2 hours, 4 hours post retreatment	1
	Retreatment 24 h	2	2
	Retreatment D8	8	3 - 11
	Retreatment D15 -2 h, -1 h, 40 min, 2 h, 4 h	Day 15 -2 hours, -1 hour predose, 40 min, 2 hours, 4 hours post dose	12 - 18
	Retreatment D22	22	19 - 25
	Retreatment D29 -2 h, -1 h, 40 min, 2 h, 4 h	Day 29 -2 hours, -1 hour predose, 40 min, 2 hours, 4 hours post dose	26 - 32
	Retreatment D36	36	33 - 39
	Retreatment D43	43	40 – End of Retreatment Visit

* See the definition for Day(s) since start of retreatment in [Section 2.1.1](#)

When multiple assessments are mapped into the same window, following rules will be applied for efficacy and safety endpoints (except ECG) and PROs:

When assessments for scheduled visit and unscheduled visit are both present within the same window, the scheduled assessments value should be used. Unscheduled visit will only be used when there is no measurement from the scheduled visit in the defined window. Two special cases need to be handled as following rule:

- When assessments on a dosing day drop to the window of a non-dosing visit, for example the dosing on Day 15 was delayed to the window of Day 22, the pre-dose assessment will be mapped to the non-dosing visit of Day 22, while the post-dose assessment will not be mapped. Unless scheduled assessments for Day 22 were performed, the scheduled ones should be mapped then.
- When assessments on non-dosing day drop to the window of a dosing visit, for example the visit Day 8 was delayed to Day 15 and no dosing was administered, assessments will be mapped to the pre-dose hour of this dosing visit. Unless the dosing were administered and scheduled assessments performed within the window, the scheduled assessments should be mapped then.

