2.11 Interim analysis

One unblinded analysis will be performed when all participants completed Day 57 (2 weeks follow-up visit after the End of Core visit on Day 43). Data from Core Period will be analyzed according to the plan herein. The optimal dose will be identified based on the dose-response relationship established by MCP-Mod, as well the sustained efficacy effect, safety profile and PK of each MIJ821 dose and regimen compared to placebo.

This unblinded interim analysis will be conducted by study team. The individual level data will maintain blinded to investigators and participants until final database lock.

3 Sample size calculation

With the randomization ratio of 2:1:2:2:2 for the biweekly dosing arms, the sample size of 27:14:27:27:27 for placebo, MIJ821 0.0048 mg/kg, MIJ821 0.016 mg/kg, 0.048 mg/kg and 0.16 mg/kg, will provide about 80% power to detect a dose-response signal [to reject the null hypothesis of a flat dose-response curve where all MIJ821 dose means are equal to the placebo mean] for the biweekly dosing arms in change from baseline in MADRS at 24 hour using MCP-Mod methodology at the one-sided $\alpha = 0.05$ level. Since MIJ821 0.0048 mg/kg is

potentially non-effective, the sample size for this arm is chosen to be 50% of other arms and is sufficient for establishing the dose-response curve.

The 6 candidates DR curves (2 Emax, 4 Sigmoid Emax) for power calculation are defined in [Section 2.4.2.](#) [REDACTED]

[REDACTED]

For the two single infusion arms of 0.048 mg/kg and 0.16 mg/kg, to maintain the same precision as for the biweekly dosing arm vs placebo, 27 participants per arm are needed. In total the study needs 177 patients. Assuming a 10% dropout rate, approximately 195 pts in total (15 pts for 0.0048 mg/kg and 30 pts for the remaining 6 treatment arms) will be randomized.

All treatment arms (including both regimen) will be included in the MCP-Mod for the primary analysis which will provide about 92% power to detect a dose-response signal in change from baseline in MADRS at 24 hour using MCP-Mod at the one-sided 0.05 level.

4 Change to protocol specified analyses

Not applicable.

5 Appendix

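### The SAP omits the protocol's laboratory shift tables to the worst on-treatment value without declaring the change, and replaces them with a by-visit count that pools new abnormalities with worsening of any size

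*SAP*

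**What the plan says.** **Protocol, Section 12.5.2, Clinical laboratory evaluations.** Besides summary statistics by visit and a listing of notable values, the protocol commits to a shift analysis: "Shift tables using the low/normal/high/ (low and high) classification based on predefined limits will be used to compare baseline to the worst on-treatment value".

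**SAP 2.6.3, Laboratory data.** The lead-in sets the layout: "following analyses will be provided for laboratory data by treatment arm and analysis visit". Three outputs follow: average change from baseline for hematology and blood chemistry, a count of participants with a newly occurring or worsening value outside the normal range, and a listing. The count has two routes in:

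- New: "For newly occurring event, the participant needs to have a baseline value that is not clinically abnormal for that parameter". A participant with no baseline value also counts as new on any abnormal result.
- Worsening: "For worsening event, the participant needs to have a baseline value that is clinical abnormal and also have a worse post-baseline value".

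Separately, liver and renal abnormalities are counted against the fixed criteria in Tables 5-3 and 5-4.

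**SAP 2.1.2, visit mapping.** For safety endpoints other than ECG: "Unscheduled visit will only be used when there is no measurement from the scheduled visit in the defined window".

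**SAP Section 4.** Under the heading "Change to protocol specified analyses" the entry is that none applies.

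**The concern.** A shift table to the worst value shows, for each participant and analyte, where the participant started and how far out of range they went at any time on treatment. SAP 2.6.3 has nothing that does this for most of the panel. What it offers instead mixes two different events in one number, does not say whether the value is too low or too high, and sets no threshold for worsening.

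The protocol (12.7) and the SAP (2.11) both name the safety profile as an input to the choice of Phase 3 dose. The analytes affected are those in protocol Table 8-4 that have no threshold table: most of hematology, electrolytes, amylase, lipase, creatine kinase, TSH, cortisol and most urinalysis items. Urinalysis is the thinnest, because the mean-change table names only hematology and blood chemistry. It is left with the pooled count, listings and the 3+ dipstick criteria, although lower urinary tract events are of special interest. Arms are small: one participant is 1/30 = 3.3 percentage points in most arms and 1/15 = 6.7 in the 0.0048 mg/kg arm.

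**Working it through.** The documents give no laboratory abnormality rate, so there is no planned figure to reproduce. The check has two parts.

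**1. Protocol and SAP side by side**

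| Feature | Protocol 12.5.2 | SAP 2.6.3 |
|---|---|---|
| Value used | Worst on treatment | Value mapped to each visit |
| Classification | Low / normal / high, with a combined low-and-high category | Outside normal range; direction not stated |
| New and pre-existing abnormality | Separated by baseline row | Pooled in one count |
| Worsening | Not measured within a category | Any worse value from an abnormal baseline |
| Unscheduled values | No exclusion stated | Left out if a scheduled value is in the window |

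Two hypothetical participants show the effect for an analyte without a threshold table, such as lipase. One is just above the limit at baseline and rises by the smallest reportable amount at Day 8: counted. The other is normal at every scheduled visit but has a grossly abnormal unscheduled sample in the Day 8 window: not counted in the table, and visible only in a listing or as an adverse event.

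The SAP does use the any-time view elsewhere. For vital signs (2.6.4.2) it plans any post-baseline abnormality and a breakdown by visit. The SAP document history logs the removal of the Holter summary, but its visible entries record no laboratory change; some entries are blacked out.

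**2. How much of the pooled count could be chance**

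Assumed, because the documents do not give them: share abnormal at baseline p = 5%, 10% or 20% (two-sided limits); within-person correlation ρ = 0.5, 0.7 or 0.9; no drug effect.

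Model: baseline x₀ = b + e₀ and visit value x = b + e, with Var(b) = ρ and Var(e) = 1 − ρ. The limits are ±c, with c = z(1 − p/2). *Worsening* means x₀ > c and x > x₀, or x₀ < −c and x < x₀. *New* means x₀ is within the limits and x is outside them. There were 400,000 simulated participants per scenario.

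Worsening rate = p × P(worse, given abnormal baseline). Worsening share = worsening / (new + worsening). For p = 10% and ρ = 0.7: 0.10 × 0.194 = 0.019, and 0.019 / (0.061 + 0.019) = 24%.

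| p | ρ | P(worse at a visit, given abnormal baseline) | New | Worsening | Worsening share |
|---|---|---|---|---|---|
| 5% | 0.5 | 0.092 | 0.040 | 0.005 | 10% |
| 5% | 0.7 | 0.165 | 0.034 | 0.008 | 20% |
| 5% | 0.9 | 0.297 | 0.020 | 0.015 | 42% |
| 10% | 0.5 | 0.122 | 0.075 | 0.012 | 14% |
| 10% | 0.7 | 0.194 | 0.061 | 0.019 | 24% |
| 10% | 0.9 | 0.317 | 0.036 | 0.032 | 47% |
| 20% | 0.5 | 0.162 | 0.134 | 0.032 | 19% |
| 20% | 0.7 | 0.232 | 0.105 | 0.046 | 31% |
| 20% | 0.9 | 0.343 | 0.062 | 0.069 | 53% |

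In participants per analyte and visit in an arm of 30, worsening by chance runs from 30 × 0.05 × 0.092 = 0.1 to 30 × 0.20 × 0.343 = 2.1.

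**Effect on power.** For a drug shift of 1 SD, 30 against 30, two-sided 0.05, per visit: 0.31–0.65 for new abnormalities alone and 0.32–0.63 with worsening added. No scenario moves by more than about 5 points, in either direction. For a 0.5 SD shift, power is at most 0.14 either way.

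**The case against.** The strongest reply is that little is lost. Mean change, listings and the liver and renal thresholds remain, and clinically significant laboratory abnormalities are reported as adverse events. The secondary safety endpoint is treatment-emergent adverse events, and the laboratory tables are descriptive. All of this stands and limits the consequence. It does not replace a per-participant worst-value table for the other analytes, nor does it make the entry in Section 4 correct. Output shells that are not public might hold a shift table, but the SAP text does not call for one.

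A second reply is that the shift table would not cure noise in worsening: high to higher stays in the same cell, and taking the worst of several samples also raises chance shifts from normal to abnormal. That is right, and is why the fix needs a separate definition of worsening.

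A reader might go further and infer that the SAP counts every numerically worse result, that the count is mostly noise, and that it hides a drug effect. The documents do not support this. The rule applies only to participants already abnormal at baseline; everyone else must cross a limit. Worsening exceeds half of the count only at the extreme of the assumed range. Per-visit power barely moves. The one clear loss (0.62 to 0.40) needs 20% abnormal at baseline, a correlation of 0.9 and a count over any of seven samples. The SAP's layout is by visit, and seven is itself an assumption (24 hours plus weekly to Day 43), because the Core laboratory rows of Table 8-1 cannot be read in the available text.

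**Conclusion.** The point holds as a discrepancy between protocol and SAP with a practical consequence. A protocol-specified safety table is not planned, the SAP says that nothing has changed, and outside the liver and renal criteria no laboratory table counts each participant once at the worst value. The replacement pools two kinds of event, gives no direction, sets no step for worsening, and can miss an extreme unscheduled result.

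These findings come from the text and need no assumption. The chance component does: 10% to 53% of the per-visit count rests on assumed baseline abnormality rates, assumed within-person correlation and normally distributed values, so its true size cannot be determined from the documents. No loss of ability to detect a drug effect has been shown for the planned layout.

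**What to change.** In SAP 2.6.3:

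1. Restore the shift table of baseline category against worst on-treatment category, by arm, with one count per participant and analyte. Include unscheduled values despite the mapping rule in 2.1.2, and state the on-treatment window.
2. Report newly occurring and worsening abnormalities in separate rows, each split into low and high.
3. Count worsening only on a prespecified step beyond baseline, for example a multiple of the limit or of the baseline value. Tables 5-3 and 5-4 supply such steps only for liver and renal parameters, so the other analytes need their own.

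If the shift table is not restored, declare and justify its removal in SAP Section 4.

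Cost: SAP wording and one standard table, from data already collected.
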